Notice: Treatment schedules shall have a standing window of allowance of +/- 3 days unless patient/logistical/medical reasons intervene. Any treatment day (radiation or drug administration) that falls on a weekend or holiday will be scheduled on the next business day. For treatment or dose modification questions, please contact [name], PhD by [contact]) or e-mail ([contact]), [name] by [contact]) or e-mail ([contact]). No investigational or commercial agents or therapies other than those described below may be administered with the intent to treat the patient's malignancy.

There will be 3 treatment groups; consisting of patients with metastatic disease in liver or lung from any primary. Safety data on Stereotactic body radiation therapy (SBRT) and ipilimumab was presented at ASTRO, 2017 (1). Based on the encouraging data on SBRT and ipilimumab, we propose to test the safety and efficacy of combination of ipilimumab or nivolumab and an anti-GITR agonistic antibody (BMS-986156) with SBRT.

The first set of subjects (group 1, 20 patients) will receive ipilimumab (3 mg/kg) plus BMS-986156 (30 or 100 mg) in order to assess safety and DLT.

The second set of subjects (group 2) will receive ipilimumab plus BMS-986156 (dose as determined in group 1) with SBRT.

Enrollment of subjects in the third set (group 3) will start at the same time as group 1.

The third set of subjects (group 3) will receive nivolumab (480 mg Q4W) plus BMS-986156 (30 mg) with SBRT.

Assessment for DLT will be done for patients enrolled on group 2; based on the outcome, dose escalation / de-escalation of ipilimumab and BMS-986156 (group 1). Treatment assignments to groups 2 and 3 will be based on disease status at enrollment and at the discretion of the PI and treating physician. In the event that a patient presents with both treatable liver and lung lesions, assignment will be based on provider preference .

All patients who achieve systemic benefit (based on physician discretion) but later progress will be given the option of receiving reinduction. Optional radiation can be administered during reinduction. If administered, radiation will be given similar to what was done in the initial treatment. After the first round of reinduction, patients may receive additional reinduction if during their most recent post cycle 4 imaging disease control is observed without severe (grade >3) toxicity. Patients with either liver or lung lesions amenable to SBRT (either 50 Gy in 4 fractions or 60 Gy in 10 fraction) will be enrolled on this trial.

Treatment group 1) Ipilimumab + BMS-986156 (30 mg / 100 mg) x 4 for safety assessment (No SBRT) → Nivolumab x 26

Treatment group 2) Sequential (late SBRT) Ipilimumab + BMS-986156 (dose as determined in group 1) x 2 → SBRT → Ipilimumab + BMS-986156 (dose as determined in group 1) x 2 → Nivolumab x 26

Treatment group 3) Concurrent (early SBRT) Nivolumab (480 mg Q4W) + BMS-986156 (30mg) + SBRT → Nivolumab + BMS-986156 x 3 (30mg) → Nivolumab x 22

Group 1, 20 patients: Ipilimumab + BMS-986156 (30 or 100 mg) Dose Escalation → Nivolumab x 26 (up to 2 year maintenance)

Day 1 and every 21 days: Ipilimumab therapy at 3 mg/kg as a 90 minute intravenous (IV) dose and BMS-986156 at either 30 mg or 100 mg dose as a 60 min IV dose will be given in an outpatient setting. Dose cycles will be repeated every 21 days: on days 1, 22, 43, and 64 for a total of 4 cycles. Maintenance therapy of Nivolumab (480mg Q4W) will start day 85 and continue every 28 days, for 26 cycles.

A modified 3+3 dose escalation then expansion to a total of 10 patients per arm (escalation + expansion, if applicable) will be performed on two dose levels of this combination therapy. Details on de-escalation are presented under section 7.7.1.

Group 1

[figure not shown]

Diagram of Treatment Schedule for Ipilimumab + BMS-986156 (30 or 100 mg) Dose Escalation → Nivolumab x 26 (Treatment Group 1)

Group 2, 20 patients: Ipilimumab + BMS-986156 x 2 → SBRT → Ipilimumab + BMS-986156 x 2 → Nivolumab x 26 (up to 2 year maintenance)

Day 1 and every 21 days: Ipilimumab therapy at 3 mg/kg as a 90 minute intravenous (IV) dose and BMS-986156 (dose as determined in group 1) as a 60 min IV will be given in an outpatient setting. Dose cycles will be repeated every 21 days: on days 1, 22, 43, and 64 for a total of 4 cycles. Nivolumab (480 mg Q4W) will start day 85 and continue every 28 days for 26 cycles. Enrollment of this group will start based on the following criteria. If 2 out of 6 patients, or less, display DLTs, then, enrollment of group 2 can begin. Alternatively, if 3 out of 6 patients, or more, display DLTs, then, enrollment of group 2 cannot begin until 10 patients have been treated in group 1.

SBRT: SBRT will be given after 2 doses of ipilimumab and BMS-986156 on days 29-32 for 50 Gy in 4 fractions or on days 29-40 for 60 Gy in 10 fractions (no SBRT during weekends): SBRT will be directed at 1-4 targetable liver or lung lesion(s). To minimize treatment breaks, patients may start radiation on a Monday.

Group 2

[figure not shown]

Diagram of Treatment Schedule for Ipilimumab + BMS-986156 x 2 → SBRT → Ipilimumab + BMS-986156 x 2 → Nivolumab x 26 (Treatment group 2).

Group 3, 20 patients: Nivolumab + BMS-986156 x 1 + SBRT → Nivolumab + BMS-986156 x 3 → Nivolumab x 22

First dose of Nivolumab + BMS-986156 and SBRT will be given concurrently (early) and followed by Nivolumab + BMS-986156 x 3; then, Nivolumab monotherapy for 22 cycles. Nivolumab will be administered for a total of 26 cycles, either as a combination or monotherapy, in this group. Enrollment of patients for this group will start around the same time as group 1. Choice of treatment group will be at the discretion of PI and treating physician.

Nivolumab therapy at 480 mg dose will be given on day 1 as a 30 minute IV dose and BMS-986156 at 30 mg dose will be given on day 1, 29, 57, 85 as a 60 min IV in an outpatient setting. Nivolumab monotherapy will start on day 113 and will continue for 22 cycles.

SBRT: SBRT will be given on days 1-4 (days 2-5 are acceptable if scheduling does not permit radiation to begin same day as infusions) for 50 Gy in 4 fractions or on days 1-12 for 60 Gy in 10 fractions (no SBRT during weekends). SBRT will be directed at 1-4 targetable liver or lung lesion(s). To minimize treatment breaks, patients may start radiation on a Monday.

Group 3

[figure not shown]

Diagram of Treatment Schedule for Nivolumab + BMS-986156 x 1 + SBRT → Nivolumab + BMS-986156 x 3 → Nivolumab x 22 (Treatment group 3)

2. Objectives

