7.1.1.1 Group 1: Dose Escalation of BMS-986156 when combined with ipilimumab

Treatment group 1: A modified 3+3 dose escalation then expansion to a total of 10 patients per arm (escalation + expansion, if applicable) will be performed on two dose levels of this combination therapy.

- The first 3 subjects will be enrolled at dose level 1 (3 mg/kg ipilimumab + 30 mg BMS-986156).
 - If 0 out of these 3 patients have a DLT, 3 patients will then be enrolled on dose level 2 (3 mg/kg ipilimumab + 100 mg BMS-986156).
 - If 1 of 3 subjects have a DLT in dose level 1 (30 mg), 3 more patients will then be enrolled at this dose level. If only 1 of the 6 total subjects at dose level 1 has a DLT, then 3 patients will then be enrolled on dose level 2, 100 mg BMS-986156.
 - Additionally, 4 patients will be enrolled on dose level 1 to a total of 10 patients at 30 mg BMS-986156.
 - If 2 of 3 subjects have a DLT at dose level 1, then dose escalation is stopped and the MTD is reached (dose level 1).
- Subjects will be receiving 3 mg/kg ipilimumab + 100 mg BMS-986156 at dose level 2.

- At this dose level, if 0 of the 3 subjects have a DLT, then both dose level 1 and dose level 2 will be expanded to more patients so that each arm has a total of 10 patients enrolled.
- If 1 of the 3 subjects at dose level 2 have a DLT, 3 more subjects will then be enrolled at this dose level. If only 1 of the 6 total subjects at dose level 2 have a DLT, both dose level 1 and dose level 2 will be expanded to more patients so that each arm has a total of 10 patients enrolled. If 2 of the 6 total subjects at dose level 2 have a DLT, then dose escalation is stopped and the MTD is reached (dose level 1). Only dose level 1 will be expanded to a total of 10 patients enrolled.
- If 2 of 3 subjects at dose level 2 have a DLT, then dose escalation is stopped and the MTD is reached (dose level 2).
- The expansion phase dose will be selected based on safety and response readouts. For example, the dose exhibiting the best therapeutic response or pharmacodynamic profile with the best safety profile.

Dose Escalation of BMS-986156 when combining with Ipilimumab.

Dose Level 1 3 mg/kg Ipilimumab + 30 mg BMS-986156

Dose Level 2 3 mg/kg Ipilimumab + 100 mg BMS-986156

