10.1. Data Set Descriptions

For group 1, after BMS-986156, dose as determined in group 1, an additional 4 patient expansion per dose level (10 patients total for each dose level) will be enrolled in that group, at the determined dose from group 1, to help determine biological endpoints. Should DLTs occur in more than 33% of patients enrolled into this expanded group, dosing at that level will be stopped. The next lower dose level will be considered the safe dose. A review of all DLTs observed will be conducted, and the need to lower the dose will be based on the discussion and agreement between the IRB and the Investigator.

All patients who receive any ipilimumab, BMS-986156, or nivolumab will be considered evaluable for toxicity.

For toxicity and response: all patients receiving at least 1 (concurrent group) or 2 (sequential group) treatment with trial drugs and completed half of the planned radiation treatment (except for group 1 where no radiation is given) will be considered evaluable for toxicity and response and included in the efficacy data set.

Group 1: (Total of 20 patients: 10 patients with 30 mg and 10 patients with 100 mg of BMS-986156, when combined with ipilimumab at 3mg/kg). Nivolumab (480mg) Q4W monotherapy will be administer for 26 cycles.

Group 2: 20 patients: trial drugs, two doses of ipilimumab (3mg/kg) combined with BMS-986156 (dose as determined in group 1) are given before SBRT. SBRT is given sequentially; followed by 2 more doses of ipilimumab + BMS-986156. Nivolumab (480mg) Q4W monotherapy will be administer for 26 cycles.

Group 3: 20 patients: First dose of trial drugs nivolumab (480 mg) and BMS-986156 (30 mg) are given concurrently with SBRT; followed by 3 doses of nivolumab (480 mg) and BMS-986156 (30 mg). Finally, Nivolumab as monotherapy for 22 cycles. Nivolumab will be administered for a total of 26 cycles in this group.

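### The group 2 start rule names no dose level and, after 3 or more of 6 DLTs, sets no DLT limit; the 33% stop in section 10.1 fills the gap only if counted over all 10 patients at a level

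*Combined protocol and SAP*

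**What the plan says.** The start rule stands in section 1, Treatment Scheme, in the Group 2 paragraph. The go branch is "If 2 out of 6 patients, or less, display DLTs, then, enrollment of group 2 can begin". The other branch is "if 3 out of 6 patients, or more, display DLTs, then, enrollment of group 2 cannot begin until 10 patients have been treated", the 10 being group 1 patients. The same paragraph assumes that a dose is already known: "BMS-986156 (dose as determined in group 1) as a 60 min IV will be given in an outpatient setting".

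Group 1 has two levels, 30 mg and 100 mg of BMS-986156, each with ipilimumab 3 mg/kg. Section 10.1 plans "an additional 4 patient expansion per dose level (10 patients total for each dose level) will be enrolled in that group". It then says "Should DLTs occur in more than 33% of patients enrolled into this expanded group, dosing at that level will be stopped", and "The next lower dose level will be considered the safe dose", with a review of DLTs between the IRB and the investigator.

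Section 7.1.1.1 governs escalation:

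- At 30 mg it covers 0 of 3, 1 of 3 and "If only 1 of the 6 total subjects at dose level 1 has a DLT". It gives no rule for 2 or more of 6.
- Also at 30 mg: "If 2 of 3 subjects have a DLT at dose level 1, then dose escalation is stopped and the MTD is reached", with dose level 1 named as that MTD.
- At 100 mg, 2 of 6 DLTs makes 30 mg the MTD, but 2 of 3 DLTs makes 100 mg itself the MTD.

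Section 7.1.1.2 starts group 2 at whichever BMS-986156 dose group 1 found to be the MTD, with ipilimumab 3 mg/kg. Section 7 opens group 2 after dose determination in group 1. Section 10 requires a report after every three evaluable patients per group and IND Office approval before dose levels change. Neither of these two gives a DLT number for opening group 2.

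**The concern.** Section 3.3 states that no clinical safety data exist for BMS-986156 with ipilimumab. Group 1 is therefore the only evidence on the pair before SBRT is added, and the start rule is the step that puts that evidence to use.

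Two things are missing from it. First, the 6 and the 10 can be read as patients at one level or as patients across both levels of group 1. Second, after at least half of six patients have had a DLT, the only written condition is a head count of 10. Whether a DLT limit also applies depends on section 10.1, whose denominator is unclear: "expanded group" could mean all 10 patients at the level or only the 4 added ones.

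At stake is adding SBRT to full-dose ipilimumab plus BMS-986156 at a level where group 1 has already shown a DLT rate above the plan's own limit.

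**Working it through.** The documents give no operating characteristics for this rule, so there is no figure to reproduce. True DLT rates p below are assumptions. Write P(x|n) for the binomial probability of x DLTs in n patients.

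**1. Observed fractions against the 33% limit.** 3/6 = 50%; 3/10 = 30%; 4/10 = 40%. Counted over 10, at most 3 DLTs pass. After 3 of 6, all 4 added patients must be DLT-free; after 4 or more of 6, the level cannot pass. Counted over the 4 added patients alone, 1/4 = 25% passes and 2/4 = 50% stops, so 3 of 6 plus 1 of 4 (4/10 = 40%) passes.

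**2. Where the branch can matter.** At 100 mg, section 7.1.1.1 already drops to 30 mg at 2 of 6, so a 100 mg level with 3 of 6 should not be carried forward. At 30 mg nothing is written for 2 or more of 6, and the section 10.1 fallback to a lower level has no group 1 level to point to.

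**3. How often it arises.** The route that section 7.1.1.1 spells out is 1 of 3, then 2 or more of the next 3: P(1|3) × P(≥2|3).

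- p = 20%: 0.384 × 0.104 = 0.040
- p = 33%: 0.444 × 0.255 = 0.113
- p = 40%: 0.432 × 0.352 = 0.152

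**4. What the denominator changes.** Given that route, the chance of ending at 4 or more of 10 is 1 − P(2|3)P(0|4)/P(≥2|3).

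- p = 20%: 1 − 0.096 × 0.4096/0.104 = 0.622
- p = 33%: 1 − 0.219 × 0.2015/0.255 = 0.827
- p = 40%: 1 − 0.288 × 0.1296/0.352 = 0.894

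A limit over all 10 stops every one of these. A limit over the 4 added patients misses those with 0 or 1 DLT among the 4: P(≤1|4) − P(2|3)P(0|4)/P(≥2|3).

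- p = 20%: 0.819 − 0.378 = 0.441
- p = 33%: 0.599 − 0.173 = 0.425
- p = 40%: 0.475 − 0.106 = 0.369

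Multiplied by step 3, the unconditional chance of a missed stop is 1.8%, 4.8% and 5.6%.

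**5. A rule that binds the limit to the start of group 2.** Open if at most 2 of 6, or if 3 of 6 is followed by 0 of 4. With six patients filled, this is P(≤2|6) + P(3|6)P(0|4).

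- p = 10%: 0.984 + 0.0146 × 0.656 = 0.994
- p = 20%: 0.901 + 0.0819 × 0.4096 = 0.935
- p = 33%: 0.687 + 0.216 × 0.2015 = 0.731
- p = 40%: 0.544 + 0.2765 × 0.1296 = 0.580
- p = 50%: 0.344 + 0.3125 × 0.0625 = 0.363

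**6. The MTD labels.** With 0 of 3 DLTs at 30 mg and 2 of 3 at 100 mg, section 7.1.1.1 names 100 mg the MTD and section 7.1.1.2 starts group 2 there, at a level with 67% observed DLTs. If the six in the start rule are the first six of group 1, the pooled count is 2 of 6 and the go branch is met as well.

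**The case against.** The strongest reply is that the sections should be read together. "Cannot begin until" states a necessary condition, not a licence to open. Section 7 requires dose determination first, 10 is the size at which the section 10.1 expansion is complete, and a level stopped at 33% cannot sensibly be the determined dose. The phrase about the expanded group also closely follows the mention of 10 patients per level. On that reading the plan already works as in step 5, and the probabilities there are its own.

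Most of this stands. A reader might infer that nothing in the plan can close group 2 after a bad result. The documents do not support that: section 10.1 has a stop and a review, section 10 requires reports and IND Office approval, and section 7.1.1.2 begins group 2 with only three patients. A reader might also take the figures in step 4 (62%, 83%, 89%) as the chance of harm. Under a count over 10 they show how often the stop would act. Nor do the go limit of 2 of 6 and the 2-of-6 stop at 100 mg contradict each other outright. The pooled example in step 6 does harm mainly through the MTD label: with that label corrected, the same counts would lead to 30 mg, where 0 of 3 had DLTs.

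What the reply does not settle is the missing dose level, the section 10.1 denominator, the absence of a fallback below 30 mg, and the two MTD labels. The start rule does not refer to section 10.1, and none of the review steps gives a DLT criterion for opening group 2.

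**Conclusion.** The point holds as an ambiguity in a safety rule together with an error in the MTD labels. It should be fixed. The start rule leaves its dose level open and relies on section 10.1 for any DLT limit after 3 or more of 6. That limit does the job only if counted over all 10 patients at the level.

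The size is moderate. The branch matters mainly at 30 mg and arises by the stated route with probability 4%, 11% or 15% at assumed DLT rates of 20%, 33% or 40%. If the 33% covers only the 4 added patients, the chance that the route occurs and the stop is then missed is about 2%, 5% and 6%. If the sponsor already means all 10, the opening probabilities of 99%, 93%, 73%, 58% and 36% (true rates of 10%, 20%, 33%, 40% and 50%, six filled) do not change. The gain is then to make the limit binding on the start rule and to correct the labels. The label error in section 7.1.1.1 does not depend on the denominator.

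**What to change.** 1. **Section 1, Group 2.** Count the 6 and the 10 at the dose level to be carried into group 2. Keep the 2-of-6 go limit. After 3 or more of 6, open group 2 at that level only if at most 3 of the 10 there have DLTs.
2. **Section 10.1.** State that the 33% applies to all patients treated at the level. With 10 planned, this means stopping at the fourth DLT. Saying so also avoids the reading that 2 of 6 (33.3%) already exceeds the limit.
3. **Section 7.1.1.1, 100 mg.** After 2 or more of 3, or 2 or more of 6, DLTs, carry 30 mg forward.
4. **Section 7.1.1.1, 30 mg.** Do not call 30 mg the MTD after 2 or more of 3 DLTs. Add a rule for 2 or more of 6: no escalation, with exactly 2 of 6 opening group 2 under the existing limit. After 2 or more of 3, or 3 or more of 6, keep full-dose group 2 closed unless at most 3 of 10 have DLTs. Otherwise hold for the section 10.1 review.

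Level -1 of section 7.1.1.2 (ipilimumab 1 mg/kg + 30 mg) can be an option for that review. It should not be the default, because it would be untested without SBRT.

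The cost is wording in three sections and no added patients. Group 2 may open later, at a lower ipilimumab dose, or not at all. A level with 3 of 6 followed by 0 of 4 would still open at full dose, as the 33% limit allows.

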2.1. Primary Objectives

- To determine the safe dose of BMS-986156 and Dose Limiting Toxicities (DLT) (30 mg vs 100 mg) when combined with ipilimumab (3mg/kg) for patients with metastatic cancer.
- To evaluate the safety and toxicity profile of ipilimumab (3mg/kg) with BMS-986156 (30 or 100 mg) administered in combination with SBRT targeting 1-4 LIVER lesion(s) for patients with metastatic cancers.
- To evaluate the safety and toxicity profile of ipilimumab (3mg/kg) with BMS-986156 (30 or 100 mg) administered in combination with SBRT targeting 1-4 LUNG lesion(s) for patients with metastatic cancer.
- To determine safety and toxicity profile of Nivolumab (480 mg) with BMS-986156 (30 mg) administered in combination with SBRT targeting 1-4 LIVER lesion(s) for patients with metastatic cancers.
- To determine safety and toxicity profile of Nivolumab (480 mg) with BMS-986156 (30 mg) administered in combination with SBRT targeting 1-4 LUNG lesion(s) for patients with metastatic cancers.

2.2. Secondary Objectives

- To determine antitumor activity of ipilimumab therapy with BMS-986156 (30 or 100mg) as well as Nivolumab with BMS-986156 (30 mg) with SBRT treatment for 1-4 lung lesions in both the SBRT treated lesion and non-irradiate tumors.

- b) To determine antitumor activity of ipilimumab therapy with or without BMS-986156 (30 or 100mg) as well as Nivolumab with BMS-986156 (30 mg) with SBRT treatment for 1-4 liver lesions in both the SBRT treated lesion and non-irradiate tumors.
- c) To compare response and progression of the non-irradiated tumors between BMS-986156 with ipilimumab vs BMS-986156 with Nivolumab, using irRC.
- d) To evaluate the predictive potential value of tumor-associated and systemic immune biomarkers for therapy effectiveness and toxicity prediction.
- e) To evaluate whether skeletal mass, neutrophil, neutrophil to lymphocyte ratio, and tumor bulk are correlated with clinical outcomes and adverse events.
- f) To evaluate whether tumor kinetics in combination with clinical correlates can help determine treatment response. The radiological response and clinical data will be analyzed using mathematical and statistical models to identify prognostic groups.
- g) To evaluate whether tumor mutational burden correlates with improved clinical outcomes and response criteria.

3. Background

Numerous clinical trials have demonstrated the ability of ipilimumab to induce long-lasting anti-tumor effects through the generation of anti-tumor immune memory (clinical trial results reviewed in). However, such evidence also suggests that ipilimumab monotherapy is effective in a limited proportion of patients. As a result, there has been interest in combining ipilimumab with other therapies including cytotoxic chemotherapy (dacarbazine)³ and other checkpoint inhibitors (nivolumab) (2). In addition, recent interest has arisen in the combination of this drug with other treatment modalities, chief among which is radiation (3-5). Mounting preclinical evidence suggests that radiation induces a tumor antigen release that activates and primes systemic T-cells for anti-tumor immunity (6). One manifestation of this immunologic effect is term the abscopal effect, which refers to systemic disease response outside of the radiation field to control limited local disease. Given that ipilimumab acts through the promotion of T-cell activity, many preclinical trials have demonstrated the abscopal effect with the combination of radiation and checkpoint inhibitors such as ipilimumab and nivolumab (7). Exemplifying such a combination, Postow et al.(5). reported marked unexpected systemic disease regression outside of a radiation field designed to palliate a paraspinal lesion in a patient with metastatic melanoma. This study and other like it offers intriguing yet anecdotal clinical evidence of the effectiveness of this combination. As a result, several phase I/II trials have begun to systematically investigate this effect (8).

3.1. Immunotherapy

3.1.1. Ipilimumab

T-cell activation is a complex process initiated when an antigen is presented to the T cell receptor (TCR) followed by the interaction of additional T cell surface molecules with their respective ligands on the antigen presenting cell (APC). This second interaction can result in a positive or a negative costimulatory signal depending on which specific molecules are involved. CTLA-4 is a T-cell surface molecule that, on interaction with the B7 molecule of the APC, leads to the termination of the T-cell response. Blockage of CTLA-4 with the monoclonal antibody Ipilimumab has led to a remarkable enhancement of the immune response in experimental models of cancer and infection (9).

Yervoy™ (ipilimumab) monotherapy has been approved for use in the US (March, 2011), the EU (July, 2011) and Australia (July, 2011) for the treatment of patients with unresectable advanced melanoma. Thousands of subjects with several cancer types in 90 completed and ongoing studies, have been treated during its clinical development program, which is focused in melanoma, prostate cancer, lung cancer, and renal cell carcinoma. In melanoma, two Phase 3 studies (**MDX010-20**

comparing ipilimumab 3mg/kg to a melanoma-specific vaccine gp100 in pretreated advanced melanoma (10) and **CA184024**, comparing ipilimumab 10mg/kg plus dacarbazine to dacarbazine alone in previously untreated advanced melanoma (11). In addition to one phase I study (Combination nivolumab, anti-PD-1 antibody, with ipilimumab (2) have demonstrated a survival benefit in patients treated with a combination of these two checkpoint inhibitors.

Over half of the patients treated with ipilimumab reported *immune-related adverse events* (irAE) defined as any AE associated with drug exposure and consistent with an immune-mediated event (thought to be a consequence of the intrinsic biological activity of ipilimumab). IrAEs predominantly involve the GI tract (manifested most often as diarrhea or colitis) and skin (pruritus and rash), and less commonly the liver (transaminase elevations), endocrine glands (manifested most often as hypophysitis/hypopituitarism), pulmonary system (cough and pneumonitis) and nervous system (motor neuropathy with or without sensory neuropathy). According to the Investigator's Brochure, most of these irAEs were clinically manageable and reversible with supportive care or corticosteroids.

Efficacy data from Phase I and II studies in melanoma suggest a trend of increasing durability and progression free survival (PFS) rates with increasing doses and duration of exposure to ipilimumab. However, preliminary data suggests that 10mg/kg of ipilimumab is associated with a higher frequency of SAEs and serious (Grade 3 or higher) irAEs than 3mg/kg of ipilimumab(2, 11, 12). It appears that an increased awareness and better management of these side effects has led to a decrease in their severity and an improvement in their control in recent trials. We propose to use ipilimumab at 3 mg/kg dose administered as 4 doses every 3 weeks and will implement a tight safety rule (see section 7.3) to stop the trial in case of excess toxicity.

It is important to note that because ipilimumab works indirectly through stimulation of the immune system by enhancing T-cell activation, its effect on tumor burden may take weeks to months to become apparent. The clinical activity of ipilimumab may manifest, not only as an early objective response, but also as stable disease (SD) with slow, continuous decline of tumor burden toward response and, in some cases, as a late objective response after initial tumor volume increase (12). For example, in one study (MDX010-19) the time to first response ranged from day 40 to day 441 (10). Durable responses and SD after treatment with ipilimumab have been observed in several malignancies, including melanoma, prostate and renal cell carcinoma.

